#### 3.2 In Hospital Visits

Enrollment activities are performed at hospital admission and during hospitalization time. After ECG & coronary angiogram required per clinical practice are performed, enrollment criteria are assessed and Patient Informed Consent will be asked to the selected patient. Demographic data, medical history, risk factors, medications and procedure information including blood and enzymes values will be collected during hospitalization.

Enrollment is possible only in case of patient eligibility (all the inclusion criteria met and all the exclusion criteria not-met) and after written consent is signed and dated by patient

(refer to Appendix H for Patient Informed Consent, PIC): the PIC is to be Local Ethical Committee approved.

Enrolment information are entered in the electronic case report form (eCRF) and authorized by the principal investigator or delegates. (Refer to “Appendix F for Data Collection Method” and refer to “Appendix G for Case Report Form” regarding patient data collected for this investigation).

All activities, performed after patient is enrolled in the investigation, are shown in the Table 2.

### **3.2.1 Procedures**

Primary PCI is performed as soon as possible, following the center clinical practice, to treat the culprit lesion. Drug Eluting Stent (DES) of choice in the center and required by the lesion anatomy will be used following the usual clinical practice. FFR and IMR will be measured at the end of the procedure.

Staged procedure to treat the non-culprit lesion will be performed before hospital discharge as per normal clinical practice of the center. FFR and IMR will be measured and lesion will be treated only if FFR will show functional stenosis. Distal lesion that can't be crossed with the guidewire will be treated as per clinical practice. Drug Eluting Stent (DES) of choice in the center and required by the lesion anatomy will be used following the normal clinical practice in each center. FFR and IMR will be measured at the end of the procedure. An ECG will be assessed approximately 90 minutes after primary PCI procedure. A TTE (Echo) will be performed before the patient discharge.

Medical therapy during the procedure and at the hospital discharge will be driven by usual clinical practice, guidelines and standard of care recommendations.

## **3.3 Follow-up Visits**

According with the study design, patients are followed for a total duration of 12 months. As per protocol, scheduled Follow Up will be at 1, 6 and 12, months after primary PCI.

### **3.3.1 One Month In-Clinic Follow Up**

One month In-Clinic Follow Up is performed by investigator or delegates as per standard practice and in accordance with the activities listed in the Table 2.

All information entered in the eCRF is authorized by the principal investigator or delegates. (Refer to “Appendix F for Data Collection Method” and refer to “Appendix G for Case Report Form” for information regarding patient data collected for this investigation).

### **3.3.2 Six Months Telephone Follow Up**

Six months Follow Up is performed by investigator or delegates in accordance with the activities listed in the Table 2.

All information entered in the eCRF is authorized by the principal investigator or delegates. (Refer to “Appendix F for Data Collection Method” and refer to “Appendix G for Case Report Form” for information regarding patient data collected for this investigation).

### **3.3.3 Twelve Months In-Clinic Follow Up**

Twelve months In-Clinic Follow Up is performed by investigator or delegates as per standard practice and in accordance with the activities listed in the Table 2.

All information entered in the eCRF is authorized by the principal investigator or delegates. (Refer to “Appendix F for Data Collection Method” and refer to “Appendix G for Case Report Form” for information regarding patient data collected for this investigation).

### **3.4 Protocol Deviation**

Investigators are required to adhere to the Investigational Plan, signed Investigator’s Agreement, applicable national or local laws and regulations, and any conditions required by the appropriate Ethics Committees or applicable regulatory authorities.

A protocol deviation is used to describe situations in which the protocol was not followed. Should a protocol deviation occur, deviation information will be recorded in hospital records provided for the investigation; then the protocol deviation information is entered in the eCRF and authorized by the principal investigator or delegates as soon as possible (Refer to “Appendix F for Data Collection Method” and refer to “Appendix G for Case Report Form” for information regarding patient data collected for this investigation).

The following details will be reported on the eCRF:

- Date of deviation
- Classification of deviation
- Deviation details
- Corrective actions

Minor deviations are defined as changes or alterations in the conduct of the trial which do not have a major impact on the subject's rights, safety or well-being, or the completeness, accuracy and reliability of the study data. Minor deviations will be notified to St. Jude Medical by the investigator within 1 month after becoming aware of the minor deviation.

Serious deviations are defined as deviations that affect patient's rights, safety, wellbeing and/or that affect the scientific integrity of the clinical investigation, including those which occur under emergency circumstances. Serious deviations will be notified to St. Jude Medical by the investigator within 3 calendar days after becoming aware of the serious deviation.

### **3.5 Adverse Events**

#### **3.5.1 Definition of Adverse Event, Adverse Device Effect, Serious Adverse Event and Serious, Unanticipated and Anticipated Adverse Device Effect**

For the purposes of the clinical report, St. Jude Medical will classify each adverse events according to ISO 14155: 2011: Clinical investigation of medical devices for human subjects - Good clinical practice.

**Adverse Event (AE)**

Any untoward medical occurrence, unintended disease or injury, or untoward clinical signs (including abnormal laboratory findings) in subjects, users or other persons, whether or not related to the medical device.

NOTE: This definition includes events related to the medical device or the comparator.

NOTE: This definition includes events related to the procedures involved.

**Adverse Device Effect (ADE)**

An adverse event related to the use of a medical device

NOTE: This definition includes adverse events resulting from insufficient or inadequate instructions for use, deployment, implantation, installation, or operation, or any malfunction of the medical device.

NOTE: This definition includes any event resulting from the use error or from intentional misuse of the medical device.

**Serious Adverse Event (SAE)**

An adverse event that led to:

- Death
- A serious deterioration in the health of the subject , that either resulted in:
  - A life-threatening illness or injury OR
  - A permanent impairment to a body structure or a body function OR
  - An in-patient or prolonged hospitalization OR
  - A medical or surgical intervention to prevent life-threatening illness or injury or permanent impairment to a body structure or a body OR
  - A malignant tumor
- Fetal distress, fetal death or a congenital abnormality or birth defect

NOTE: A planned hospitalization for a pre-existing condition, or a procedure required by the CIP without serious deterioration in health, is not considered a serious adverse event.

**Serious Adverse Device Effect (SADE)**

An adverse device effect that has resulted in any of the consequences characteristic of a serious adverse event.

**Unanticipated Serious Adverse Device Effect (USADE)**

A serious adverse device effect which by its nature, incidence, severity or outcome has not been identified in the current version of the risk analysis report.

**Anticipated Serious Adverse Device Effect (ASADE)**

A serious adverse device effect which by its nature, incidence, severity or outcome has been previously identified in the risk analysis report.

### 3.5.2 List of Possible Adverse Events and Adverse Device Effects

There are no obvious risks associated with the study conduction.

Possible adverse device effects and adverse events include but are not limited to those foreseen with other normal coronary guidewire use and with normal PCI procedure.

Potential complications which may be encountered during all catheterization procedures include but are not limited to: vessel dissection or occlusion, perforation, embolus, spasm, local and/or systemic infection, pneumothorax, congestive heart failure, myocardial infarction, hypotension, chest pain, renal insufficiency, serious arrhythmias or death.

### **3.5.3 Procedure for assessing, recording and reporting Adverse Events, Adverse Device Effects, Serious Adverse Events and Serious Adverse Device effects**

Safety surveillance and reporting will be done for all patients enrolled in this study.

Safety surveillance within this clinical investigation and safety reporting, both performed by the investigator, starts as soon as the patient is enrolled in this clinical investigation (date of signature of the informed consent). The safety surveillance and the safety reporting will continue until the last follow-up visit has been performed or the patient is deceased or the patient/investigator concludes his participation into the clinical investigation.

NOTE: If an adverse event is documented at the patient's last follow up visit, both the notification and follow-up information on the AE CRF are to be provided to the sponsor.

- All serious Adverse Events and all Adverse Device Effects (serious or non-serious) are to be documented and reported to the sponsor maximum 3 calendar days after becoming aware of the event.
- Non-serious adverse events documentation and reporting are limited to cardiovascular and neurovascular events and to events endpoints related.

Should an AE occur, record AE information in the hospital records, document the information into the adverse event form as soon as possible. By completing the form, the sponsor will be notified. Refer to Table 1: Data Collection and Appendix F for Data Collection Method. In case of EDC failure, notify Sponsor via Fax ([contact]) or via [[contact]](mailto:[contact]).

Sponsor will be responsible for ensuring the assessment of immediate AE 'reportability' or 'non-reportability' to the competent authorities. All the reported AEs will be documented and reported in a periodic report.

Additional information may be requested, when required, by the sponsor in order to support the reporting of AEs to regulatory authorities and to support AE analysis. The investigator must notify the EC, if appropriate, in accordance with national and local laws and regulations, of the AEs reported to the sponsor.

In case of disagreement between sponsor and investigator in the AE assessment, then both assessments will be reported.

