### **3.6 Early Conclusion of Patient Participation**

All reasonable efforts should be made to retain subjects within the clinical trial until completion of the required period of participation. In addition to withdrawal following completion of the clinical trial, reasons for withdrawal include, but are not limited to the following:

- Patient and/or Family Request
- Patient Lost to Follow-Up
- Patient Withdrawn by Investigator
- Patient Withdrawn by Sponsor
- Patient Death

In case of withdrawal the Sponsor will be notified filling the Termination eCRF.

All information entered in the eCRF is authorized by the principal investigator or delegate. (Refer to "Appendix F for Data Collection Method" and refer to "Appendix G for Case Report Form" for information regarding patient data collected for this investigation).

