## 4 Scientific Soundness

### 4.1 Sample Size

Study aim is to assess/explore, in a cohort of STEMI patients at 1 year of follow-up from primary PCI, if categorization of IMR based on the median value can be considered a predictive / prognostic for the occurrence of cardiovascular events such as death, re-MI, re-hospitalization for HF, resuscitation or appropriate ICD shocks.

It is believed, based on the events reported in similar cohort of patients , that the expected events at one year should be of 12-16%.

The present study aims to demonstrate that the incidence of events is significantly different in the two subpopulations of patients with IMR upper and lower of the value of 32, found by Fearon et al.; other authors found the median value as event predictor.

Based on these assumptions, hypothesizing an incidence of events/year by 7% in the group of patients with IMR values below its median and 21% in the group with higher values of IMR, with an alpha error = 0.05, a power of 85% and applying the two tails Chi-square test, it is estimated that 218 patients are needed.

Providing a dropout rate of 10%, the number of patients who must be enrolled will be 242.

It is assumed that the participant centers will be up to 20. Based on number of cases in previous year evaluation, enrollment mean rate is assumed to be approximately 6-10 patients/year/center.

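### Endpoint collection can stop when the investigator ends a patient's participation, and no 1-year status is sought afterwards from patients who have not refused it

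*Combined protocol and SAP*

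**What the plan says.** Section 3.5.3 starts safety surveillance and reporting at consent and continues it until the last follow-up visit, "or the patient is deceased or the patient/investigator concludes his participation into the clinical investigation". The same section sends endpoint events down this route. All serious adverse events are reported, and for the rest "Non-serious adverse events documentation and reporting are limited to cardiovascular and neurovascular events and to events endpoints related".

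Section 3.6 opens with a retention aim: "All reasonable efforts should be made to retain subjects within the clinical trial until completion of the required period of participation". Its list of withdrawal reasons, which is expressly not exhaustive, includes "Patient Withdrawn by Investigator" and "Patient Withdrawn by Sponsor". No grounds or time limits are given for either. The action required is: "In case of withdrawal the Sponsor will be notified filling the Termination eCRF".

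Table 2 (section 3.1) makes the 6-month contact a telephone call and the 12-month contact in-clinic. Section 3.3.3 says "Twelve months In-Clinic Follow Up is performed by investigator or delegates as per standard practice" and gives no alternative for a patient who cannot attend.

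The primary endpoint (section 2.2.1) is a composite at 1 year. Section 4.2 tests it by chi-square, IMR above against below the median, with no rule for patients whose 1-year status is unknown. Section 4.1 allows for loss by number only: "Providing a dropout rate of 10%, the number of patients who must be enrolled will be 242".

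**The concern.** The stopping sentence is written for safety, but it reaches the primary endpoint. The documents describe two ways of learning about events, the scheduled visits and adverse-event reporting, and both end when participation is concluded.

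The design gives no reason for this. Culprit IMR is recorded at the end of primary PCI, any staged procedure takes place before discharge, and medical therapy follows usual practice (section 3.2.1). After discharge there is no study treatment to discontinue. A patient whose IMR is recorded, and who has not refused data collection, can still supply the outcome the study needs.

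Withdrawal by an investigator would usually come after IMR is known and may depend on the patient's condition. Removal could then be related to both IMR and events, which biases the comparison. Adding patients makes up lost numbers but does not correct selective loss, and no analysis can recover events that were never collected. The Kaplan-Meier and Cox analyses in section 4.2 can censor at withdrawal, but they are secondary, and censoring does not supply the missing 1-year status.

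**Working it through.** **Inputs (section 4.1).** Event rates 7% and 21%, groups split at the median, two-sided alpha 0.05, power 85%, 218 evaluable, 10% dropout, 242 enrolled.

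**The plan's own figure.** Pooled two-proportion formula without continuity correction, with mean rate p̄ = 0.14:

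n per group = [1.960·√(2·0.14·0.86) + 1.036·√(0.07·0.93 + 0.21·0.79)]² / 0.14² = (0.962 + 0.498)² / 0.0196 = 108.7, so 109 per group and 218 in total. This matches. For dropout, 218/0.9 = 242.2, which agrees with 242 to within rounding.

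**Power formula.** Φ[(d − 1.960·s0)/s1], where d is the difference in rates, s0 = √(p̄(1−p̄)(1/n1 + 1/n2)) and s1 = √(p1(1−p1)/n1 + p2(1−p2)/n2).

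- All 242 with known status (121 per group): expected events 121 × 0.07 = 8.47 and 121 × 0.21 = 25.41, total 33.9; power 0.886.
- 24 lost, 12 per group, at the same risk as their group: 12 × 0.07 + 12 × 0.21 = 3.4 events uncollected; rates stay at 7% and 21% in 109 per group; power 0.851.

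**If those lost are at higher risk.** The splits and the doubled risk (14% low IMR, 42% high IMR) are assumptions, because the documents give neither. All events among those lost are taken as uncollected, which assumes loss soon after discharge.

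| Lost (low/high IMR) | Events lost | Low group observed | High group observed | Power |
|---|---|---|---|---|
| 2/4 | 0.28 + 1.68 = 2.0 | 8.19/119 = 6.9% | 23.73/117 = 20.3% | 0.857 |
| 12/12 | 1.68 + 5.04 = 6.7 | 6.79/109 = 6.2% | 20.37/109 = 18.7% | 0.80 |
| 8/16 | 1.12 + 6.72 = 7.8 | 7.35/113 = 6.5% | 18.69/105 = 17.8% | 0.73 |

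At 1.5 times the group risk, power is 0.83 (12/12) or 0.80 (8/16). At 2.5 times it is 0.77 or 0.65.

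**Outer limits on the result.** Suppose 8/109 against 23/109 is observed (p = 0.004) with 12 unknown in each group. Counting every unknown low-IMR patient as an event gives 20/121 against 23/121 (p = 0.61). Counting every unknown high-IMR patient as an event gives 8/121 against 35/121 (p < 0.0001). These extremes are implausible, but they show that the planned amount of missing status could decide the answer.

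**The case against.** The strongest reply is that the text shows a gap but does not show that anyone will fall into it. No section says a patient found ineligible late is to be withdrawn. Surveillance applies to every enrolled patient, deviations are already logged under section 3.4, and section 3.6 asks sites to retain patients. The consent form and CRF are not in the text reviewed, so consent may already permit record checks, and the Termination eCRF may already separate refusing visits from refusing all data. All of this stands. It limits how large the problem may be, but it supplies no written step that collects outcomes after withdrawal.

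Several stronger readings are tempting and should not be made:

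- **That a missed 12-month visit ends knowledge of events at about 6 months.** It does not. Participation has not been concluded, surveillance continues, serious events are due within 3 calendar days of awareness, and deaths within 72 hours (section 3.7). What is missing is a planned contact, so later events depend on what the site happens to learn.
- **That the stopping sentence covers the sponsor.** It names only the patient and the investigator. Sponsor withdrawal comes from the list in section 3.6.
- **That culprit IMR is the only study measurement and everything else is usual care.** IMR is also measured at the staged procedure, and FFR decides whether non-culprit lesions are treated (section 3.2.1). The narrower statement holds: there is no continuing study treatment after discharge.
- **That all 24 planned dropouts are due to this rule.** The list also contains patient or family request and loss to follow-up. The fix exempts refusals and cannot guarantee that lost patients are found.

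**Conclusion.** The point holds as an avoidable gap in outcome collection. As written, an investigator's or sponsor's decision can remove a patient from the 1-year endpoint after IMR is known, without that patient refusing anything, and nothing recovers the outcome. The missing telephone option at 12 months is a separate, smaller gap.

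The size cannot be fixed from the documents. A reader might infer that the study is underpowered, but that is not shown. Loss of up to 10% unrelated to outcome leaves 0.851, and six withdrawals split 2/4 at doubled risk leave 0.857. The figures of 0.80 and 0.73 are bounds that need all 24 dropouts to be lost at doubled risk, and 0.73 also needs the 8/16 split. The 0.886 with complete status is a ceiling, not the expected gain from the fix. The main concern is selective loss: if sicker high-IMR patients leave more often, the observed contrast shrinks (11.3 instead of 14 percentage points in the 8/16 case), and no later analysis can restore it. This is a low-cost improvement worth making.

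**What to change.** - **Section 3.5.3:** end endpoint-event collection only at the 12-month assessment, at death, or when the patient withdraws consent to further data collection.
- **Section 3.6:** state that investigator or sponsor withdrawal after culprit IMR is recorded does not end outcome collection. Log eligibility breaches found later as deviations under section 3.4 and continue follow-up to 12 months.
- **Section 3.6, patients who stop or miss visits without refusing data collection:** obtain 12-month vital status and composite events by telephone or from hospital records. Record on the Termination eCRF whether visits only or all data are refused.
- **Section 3.3.3:** allow the clinical and event part of the 12-month assessment by telephone when the patient cannot attend. Only the in-person items, chiefly the echocardiogram, would then be missing.

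Cost: an amendment under section 6.3, with ethics approval and protocol signatures, across up to 20 centres. Enrolment began in June 2013, so patients already enrolled may need to re-consent where their consent does not cover telephone contact and record checks. Existing site staff would make a small number of calls and request source documents for events learned by telephone; even if every planned dropout needed a check, that is about 24 patients.

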### **3.6 Early Conclusion of Patient Participation**

All reasonable efforts should be made to retain subjects within the clinical trial until completion of the required period of participation. In addition to withdrawal following completion of the clinical trial, reasons for withdrawal include, but are not limited to the following:

- Patient and/or Family Request
- Patient Lost to Follow-Up
- Patient Withdrawn by Investigator
- Patient Withdrawn by Sponsor
- Patient Death

In case of withdrawal the Sponsor will be notified filling the Termination eCRF.

All information entered in the eCRF is authorized by the principal investigator or delegate. (Refer to "Appendix F for Data Collection Method" and refer to "Appendix G for Case Report Form" for information regarding patient data collected for this investigation).

### **3.7 Patient Death**

In case of patient death, all death information has to be recorded in either hospital records or the patient death worksheet provided for the investigation and immediately entered in the corresponding eCRF and authorized by the principal investigator or delegates (Refer to "Appendix F for Data Collection Method" and refer to "Appendix G for Case Report Form" for information regarding patient data collected for this investigation): it is Investigator's responsibility to inform the sponsor within 72 hours of becoming aware of the death. It is also Investigator's responsibility to notify the ECs, according to their required timelines.

It is Sponsor's responsibility to inform the competent authorities, locally and nationally as required.

The patient death eCRF must always be accompanied with the documentation of pertinent events; furthermore completing the appropriate eCRF (Adverse Event, Death and Termination) must be completed.

The following information will be reported on the patient death eCRF:

- Date of death.
- Place death occurred (e.g. hospital, nursing home, patient's home)
- If death was witnessed
- Cause of death
- Any other circumstances surrounding the death
- Approximate time interval to death from the initiating event (e.g. sudden, non sudden)
- Autopsy report (if performed)

